2.3. Study Endpoints

All safety and efficacy endpoints described will be adjudicated in a blinded manner by the Clinical Events Committee (CEC). An Independent Data Monitoring Committee (IDMC) will monitor safety throughout the duration of the study.

2.3.1. Primary Safety Endpoint

The primary safety endpoint is a combination of major bleeding events and CRNM bleeding events per ISTH definition, occurring during the Main Treatment Period: from the date of first dose of study drug to the Month 3 Visit, or to the date of last dose of study drug plus 3 days if study treatment is discontinued, whichever is earlier.

2.3.2. Secondary Safety Endpoint(s)

The secondary safety endpoints are:

• All bleeding events occurring during the Main Treatment Period: from the date of first dose of study drug to the Month 3 Visit, or to the date of last dose of study drug plus 3 days if study treatment is discontinued, whichever is earlier.

- A combination of major and CRNM bleedings from the day after Month 3 Visit to the date of the last dose of study medication plus 30 days for subjects who participate in the Extension Period.
- All bleeding events from the day after the Month 3 Visit to the date of last dose of study medication plus 30 days for subjects who participate in the Extension Period.

2.3.3. Secondary Efficacy Endpoints

The secondary efficacy endpoints are:

- The combination of symptomatic TE in the systemic arterial or venous pathways including DVT, PE, stroke, intracardiac thrombus, SEE, and MI, and asymptomatic intracardiac thrombus identified by cardiac imaging, that occur from randomization to the Month 3 Visit.
- Deaths as a result of TE that occurs from randomization to the Month 3 Visit.
- All-cause mortality from randomization to the Month 3 Visit.
- The combination of symptomatic TE in the systemic arterial or venous pathways and asymptomatic intracardiac thrombus identified by cardiac imaging, which occur from the day after the Month 3 Visit to the date of the last dose of study drug plus 30 days for subjects who participate in the Extension Period.
- Deaths as a result of TE that occurs from the day after Month 3 Visit to the date of the last dose of study drug plus 30 days for subjects who participate in the Extension Period.
- All-cause mortality from the day after the Month 3 Visit to the date of the last dose of study drug plus 30 days for subjects who participate in the Extension Period.

2.3.4. Pharmacokinetic (PK)/Pharmacodynamic (PD)/Biomarker Endpoint(s)

Plasma concentrations of edoxaban and its metabolite, D21-2393, will be assessed in subjects who receive at least 1 dose of edoxaban treatment and have measurable concentrations of edoxaban and/or D21-2393. Population PK analysis will be conducted to characterize the PK profiles of edoxaban in this target subject population.

The PD biomarkers of coagulation, PT, activated partial thromboplastin time (aPTT), and antiactivated Factor X (FXa), will be assessed as secondary endpoints in edoxaban-treated subjects.

Other biomarkers may be tested related to coagulation and/or edoxaban's mechanism of action.

2.3.5. Quality of Life Assessment

A pediatric QOL questionnaire will be issued at randomization and at the end of the Main Treatment Period to assess such categories as: health and activities, feelings about themselves, relationships with others, and school behavior. Note the QOL can be filled out by either a parent or the study participant. The same person should complete the QOL at Month 3.

PedsQL version 4.0, generic core scale will be used in the study.

The following questionnaires will be used:

- Adolescent (13-18) Self report
- Adolescent (13-18) Parent report
- Child (8-12) Self report
- Child (8-12) Parent report
- Young child (5-7) Self report
- Young child (5-7) Parent report
- Toddler (2-4) Parent report

3.2. Discussion of Study Design

This study is designed to compare the safety of edoxaban with SOC in pediatric subjects with cardiac conditions at risk of thromboembolic events. The adjudication of the efficacy and safety endpoints will be conducted by a blinded adjudication committee.

The study includes 2 periods.

• The Main Treatment Period is defined as the time from randomization, until the end of Month 3 of treatment.

Subjects who discontinue treatment from the Main Treatment Period prior to Month 3 will continue to be followed monthly according to the Schedule of Events (Appendix 17.1) through the Month 3 visit (Visit 5), and have a 30-day Follow-Up Visit. If treatment discontinuation occurs prior to Month 2 visit, the 30-day Follow-Up Visit will occur on the same day as the Month 3 visit.

Subjects who complete the Main Treatment Period (Month 3) but do not continue into the Extension Period will have a Month 3 Visit and a Follow-Up Visit, 30 days after last dose of study drug and be discontinued from the study.

Subjects who withdraw from the study prior to Month 3 (meaning the subject can no longer participate in the study due to withdrawal consent), will have a Follow-Up phone call 3 months from the date of randomization to ascertain any events (TE and/or bleeding events) that may have occurred since withdrawal.

• The Extension Period is discretionary for the subject based on the Investigator judgment of risk burden and will include treatment from the end of the Main Treatment Period (Month 3, Visit 5) up through the end of Month 12 (Visit 8).All subjects entering the Extension Period will be given edoxaban for the duration of the Extension Period.

After Month 3, all subjects will be transitioned to edoxaban at the appropriate dose for their age and weight at informed consent.

Subjects who discontinue the treatment and study at any time after Month 3 will have a Discontinuation Visit performed with a subsequent 30-day Follow-Up.

Subjects who complete Extension Period treatment at Month 12 (Visit 8) will have a Follow-Up Visit, 30 days after last dose of study drug (Visit 9).

Subjects who require anticoagulant treatment after discontinuation of the study treatment at any time will be transitioned to a therapy as determined by the Investigator (Appendix 17.7).

About 150 subjects from sites selected globally will be randomized in a 2:1 ratio (edoxaban:SOC, respectively) ratio into this study.

Subjects from 1 to <18 years of age will be enrolled in the study as soon as the dosing regimen is established for each age cohort in the Phase 1 single-dose U157 study. U157 has 5 dosing age cohorts that are similar to the U313 study:

- Ages 12 to <18 years
- Ages 6 to <12 years
- Ages 2 to <6 years

• Ages 6 months to <2 years

(In Cohort 4 [6 months to <2 years], enrollment may open after the protocol data requirement for IDMC review for subjects less than 1 year old is met and the IDMC reviews and approves the data. Sites will be notified that enrollment of 6 month olds to <1 year olds may also open.)

• Ages birth to <6 months.

A review of safety data of 10%, 25%, 50%, and 75% of subjects completing the Main Treatment Period of 3 months will be performed on a routine basis by the Independent Data Monitoring Committee (IDMC). In addition, the IDMC will review the edoxaban exposure analysis from the U157 study in addition to the safety data from each age cohort to approve the proposed dose for the same age cohort in the U313 study.

Additionally, subjects less than 1 year of age will be admitted to the study after review by the IDMC of safety data of 50% of subjects in the 1 to <18 years of age group who have completed the Main Treatment Period of 3 months (50 subjects in edoxaban arm and 25 subjects in SOC arm).

3.3. End of Study

This study will continue to randomize subjects until approximately 150 subjects (100 edoxabanand 50 SOC-treated subjects) complete at least 3 months of treatment. All subjects in the Extension Period will complete treatment as judged by the Investigator after the last subject is randomized and completes 3 months of treatment.

Primary safety endpoints are achieved during the first 3-month treatment period, ie, safety (bleeding) events occur across both treatment groups for the safety analysis set during the first 3-month treatment period anytime from the date of first dose of study drug through the final Month 3 Visit in all randomized subjects who receive at least one dose of randomized study drug. Based on the End of Randomization date a global End of Treatment (EOT) date will be established that ensures a minimum of 3 months of treatment for the last subject(s) randomized to study. All subjects must permanently discontinue study treatment on or before the EOT date. A final Follow-Up Visit date will be set 1 month following the EOT date. All subjects must complete their Follow-Up Safety Visit and permanently discontinue study on or before the Follow-Up Visit date. All subjects that discontinue treatment at Month 3 based on EOT will be placed on SOC at Investigator discretion. All safety and efficacy events will be evaluated by the CEC. Adjudicated results will be the basis for the final analyses.

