adjusted. Subjects who are ≥ 60 kg of body weight at consent and drop below that body weight will receive 45 mg dose at any subsequent visit. Subjects ≥ 30 and < 60 kg at consent increasing their weight to ≥ 60 kg will increase their dose to 60 mg.

^c Edoxaban dosage regimen will be reduced permanently for subject with body weight <5th percentile for age. Refer to Appendix 17.11.

^d Per Principal Investigator's discretion, for subjects in Cohort 2 that require either 45 mg or 60 mg dose, the Principal Investigator may use edoxaban tablets instead of granules, if they wish.

^e Edoxaban granulation will be diluted with 8 mL water to provide a concentration of 6 mg/mL dosing suspension. If body weight increases or decreases from the categories of weight defined at consent, the subject will be dose adjusted. Subjects who are ≥60 kg of body weight at consent and drop below that body weight will receive 45 mg dose at any subsequent visit. Subjects ≥30 and <60 kg at consent increasing their weight to ≥60 kg will increase their dose to 60 mg.

Note: Dose is based upon weight at corresponding visit.

For subjects without prior anticoagulant therapy, edoxaban may be started the day of randomization (Day 1).

Proprietary and Confidential Page 55 For subjects who received VKA treatment prior to randomization and are randomized to edoxaban, VKA treatment will be discontinued the day before randomization and edoxaban dose will be initiated when an INR \leq 2.5 is reached.

5.1.1.2. Standard of Care Treatment Arm (Randomization to Month 3).

SOC randomized subjects will be treated with SOC though Month 3 (Visit 5) and then offered edoxaban through Month 12. SOC treatment will be packaged and dispensed to the subject on a monthly visit schedule. After Month 3, all subjects will be transitioned to edoxaban at the appropriate dose for their age and weight. Locally sourced SOC is the preferred option for this study, either by the Investigator or, alternatively local supply depots within each country that provide SOC directly to the clinical sites. However, centrally sourced SOC can be provided when the country or clinical site requirements deem it necessary. In the case of centrally sourced treatment, the Sponsor will only provide enoxaparin as LMWH and warfarin as VKA.

For subjects who did not receive VKA treatment prior to randomization and are randomized to SOC with VKA, VKA treatment may be started on the day of randomization (Day 1).

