6.4.4. Month 3 (Visit 5; End of Main Treatment Period) Procedures

All randomized subjects including those that have discontinued treatment prior to Month 3 will have an EOT assessment at Month 3.

Note: if there was a symptomatic thrombotic event experienced by the subject prior to Month 3 documented by the appropriate imaging, a Month 3 echocardiogram is not necessary since the subject has met an event endpoint.

The following will be performed at this visit:

• Perform physical examination (Section 9.9) including:

Vital signs (BP, heart rate, and body temperature after resting in a sitting or supine position [Note: the appropriate cuff size base on arm circumference will be used.])

Height and body weight (may be performed by an Investigator or other healthcare provider designated by the Investigator).

- Review concomitant medications
- Count unused study drug tablets/bottles/syringe and calculate compliance
- Safety review for AEs/SAEs
- Review for symptomatic endpoint events (bleeding, symptomatic TE with appropriate imaging)
- Complete the QOL Questionnaire. Note: the QOL can be filled out by EITHER a parent or the study participant. The same person should complete the QOL at Month 3.
- Take samples for the following:

LFTs (ALT, AST, TBL, and ALP)

Serum creatinine and eGFR assessment

Hematology

Urine pregnancy test (for females of childbearing potential)

- Discretionary anti-FXa level and/or aPTT measurement for subjects on SOC with heparin and INR assessment for the subjects on SOC with VKA
- At the Investigator's discretion to extend the study, dispense edoxaban study drug medication and review dosing instructions per subject/parent(s)/guardian(s)'s request.
- Perform echocardiogram to evaluate presence of asymptomatic thrombosis. Note: if there was a symptomatic event experience by the subject prior to Month 3 documented by the appropriate imaging, a Month 3 echocardiogram is not necessary since the subject has meet an event endpoint.

6.5. Extension Period (beyond Month 3 – Month 6, 9, and 12; Visits 6, 7, and 8)

At the Investigator's discretion, study treatment can be extended up to 12 months. All subjects will be offered edoxaban treatment for the duration of the Extension Period based on the Investigator's judgment of the subject's potential thrombotic burden.

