11.4.3. Safety Analysis

11.4.3.1. Analysis of Bleeding Events

The primary safety endpoint is the composite of major and CRNM bleeding events that occur during the Main Treatment Period: from the date of first dose of study drug to the Month 3 Visit, or to the date of last dose of study drug plus 3 days if study treatment is discontinued, whichever is earlier. This analysis will be based on CEC adjudication results.

The time to major or CRNM bleeding occurring during the Main Treatment Period will be compared between treatment groups for subjects in the Safety Analysis Set, using the Cox proportional hazards regression model with treatment group, concomitant usage of aspirin at baseline, and underlying disease (Kawasaki disease, Fontan surgery, heart failure or Other) as covariates. Hazard ratio between edoxaban and SOC treatment group will be calculated with corresponding 95% CI. The incidence, annualized event rate, and rate difference between edoxaban and SOC treatment groups will also be calculated.

In addition, incidence, annualized event rate and rate difference between edoxaban and SOC treatment groups with corresponding 95% CI will be calculated for following endpoints for Safety Analysis Set for the Main Treatment Period. Incidence and annualized event rate will also be calculated for the following endpoints occurring from the day after Month 3 Visit to date of last dose of study drug plus 30 days in the Extension Period.

- Major and CRNM bleeding event combined
- Major bleeding event
- All bleeding event (major, CRNM, and minor bleeding combined)

The above 3 categories of bleeding endpoints will also be summarized for the periods and subjects below:
- Incidence, annualized event rate, and rate difference will be calculated for events occurring from the date of first dose of study drug to the date of last dose of study drug plus 30 days for subjects who do not participate in the Extension Period.
- Incidence and annualized event rate will be calculated for events occurring from the day after Month 3 Visit to the data of last dose of study drug for subjects who participate in the Extension Period.

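### Section 3.3 gives two stopping rules for the Extension, Section 5.1.1.2 ignores the global end-of-treatment date, and crude Extension incidence is then not a risk over any defined period

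*Combined protocol and SAP*

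**What the plan says.** Section 3.3 (End of Study) makes two statements about when Extension treatment ends. Its first paragraph says that Extension subjects "will complete treatment as judged by the Investigator after the last subject is randomized and completes 3 months of treatment". Its second paragraph derives a global EOT date from the end of randomization, one that "ensures a minimum of 3 months of treatment for the last subject(s) randomized to study", and then states: "All subjects must permanently discontinue study treatment on or before the EOT date". It also foresees subjects who get no Extension at all: "All subjects that discontinue treatment at Month 3 based on EOT will be placed on SOC at Investigator discretion".

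Elsewhere the Extension is described without reference to an EOT date. Section 5.1.1.2 says: "SOC randomized subjects will be treated with SOC though Month 3 (Visit 5) and then offered edoxaban through Month 12". Section 6.5 says "All subjects will be offered edoxaban treatment for the duration of the Extension Period", subject to the Investigator's judgment of thrombotic burden. Sections 3.2 and 6.5 treat Month 12 as an upper limit. Sections 5.6.2 and 6.5 let a subject stop treatment and study at any time after Month 3. The synopsis gives individual participation as 4 to 13 months and total study duration as about 3 years.

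For analysis, Section 11.4.3.1 says of the bleeding endpoints: "Incidence and annualized event rate will also be calculated for the following endpoints occurring from the day after Month 3 Visit", up to last dose plus 30 days. Section 11.4.1.1 plans the same two summaries for thromboembolic events (TE), death from TE and all-cause mortality. Section 11.1 restricts the Extension analyses to subjects who enter the Extension and take only edoxaban in it.

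**The concern.** Within Section 3.3, one sentence leaves the stop to the Investigator after a milestone, and the other imposes a calendar stop that may fall on that same milestone. A site reading Section 5.1.1.2 alone would expect Month 12 to be available to every SOC subject who continues. Under the EOT rule it may not be.

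The statistical consequence concerns the Extension secondary endpoints. Section 11 does not define incidence; I read it as the proportion of participants with at least one event. When participants are observed for different lengths of time, that proportion has no stated time horizon. It depends on how long people happened to be followed as well as on their risk. The only time-to-event method in Section 11 is the Cox model for Main Treatment Period bleeding, so no estimate that allows for censoring is planned for the Extension. The Extension safety figures would be hard to interpret alone and hard to set beside other studies.

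**Working it through.** **The plan's own figure.** Main period, Extension and follow-up give 3 + 0 + 1 = 4 months at least and 3 + 9 + 1 = 13 months at most. The stated 4 to 13 months reproduces and implies 0 to 9 months of Extension.

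**Time at risk in the Extension analyses.** Subjects with no Extension are outside these analyses (Section 11.1), and the window adds 30 days after last dose. Time at risk is therefore about 1 to 10 months.

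**Share cut by the EOT date.** The documents give no accrual curve, so these are assumptions: uniform accrual over A months, all 150 subjects entering the Extension, and nobody stopping for other reasons. If the EOT date falls D months after the last randomization (D from 3 to 12), the share losing some of the 9 months is (12 − D)/A.

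- Earliest permitted date, D = 3, with A = 36 − 3 − 1 = 32: 9/32 = 28%, about 42 of 150. Mean available Extension is 9 − 4.5 × 9/32 = 7.7 months.
- A from 33 down to 18 months, D = 3: 27% to 50%.
- D = 6, A = 32: 6/32 = 19%. D = 12: none.

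A 3-year study also fits 23 months of accrual with an EOT at the last subject's Month 12 (23 + 12 + 1 = 36), in which case nobody is cut. The text does not say which applies.

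**Effect on crude incidence (A = 32, D = 3).** Assume a constant hazard with a 9-month risk of 10%: λ = −ln(0.9)/9 = 0.0117 per month. Let w = 30 days = 0.986 month.

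- Full Extension: 1 − exp(−λ(9 + w)) = 11.0%.
- Mean over truncated subjects: 1 − [exp(−λw) − exp(−λ(9 + w))]/(9λ) = 6.2%.
- Reported: 0.719 × 11.0% + 0.281 × 6.2% = 9.7%.
- Standard error at n = 150: √(0.110 × 0.890/150) = 2.6 points. Shift: 1.37/2.56 = 0.53 SE, or 0.44 SE if only 100 enter.
- With a 9-month risk of 20%: 21.9% becomes 19.3%, or 0.78 SE at n = 150. At A = 18 the shifts are 0.95 SE (10% case) and 1.39 SE (20% case).

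**Late entrants.** Section 3.2 admits infants under 1 year only after review of 50 + 25 older children who completed Month 3. Under uniform accrual with immediate review, that is month 32/2 + 3 = 19. Of entrants after that point, 9/13 = 69% are truncated. Their mean Extension is 5.9 months against 9.0 for earlier entrants, and in the 10% case their crude incidence is 7.7% against 11.0%. The annualized rate is the same in both groups, 12 × 0.0117 = 0.14 per year, because the hazard was assumed constant.

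**The case against.** The strongest reply is that the plan already deals with unequal follow-up. An annualized rate accompanies incidence for every Extension endpoint, and Section 11.3 summarises Extension exposure and tabulates discontinuations by reason. This largely stands. The rate is a valid summary of events per exposure time, and a constant hazard is needed only to compare or extrapolate across unequal windows. It does not give the reported incidence a time horizon, and Section 11 does not define its person-time denominator.

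The second reply also stands. Month 12 is a ceiling in Sections 3.2 and 6.5, the Extension is discretionary, and stopping is allowed at any time. A ceiling and an earlier cut-off can coexist, and follow-up would be unequal without any EOT rule. The textual conflict is therefore confined to Section 3.3 against itself and the unconditional offer in Section 5.1.1.2.

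A reader might go further and infer three things that the documents do not support:

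- That the Extension incidence is a 9-month risk reported with bias. No passage gives it that target; the window is defined by last dose plus 30 days.
- That the EOT date is the last subject's Month 3. The text sets a minimum, so this is only the earliest possible date.
- That infants are shown to fare worst. Staged entry makes the direction plausible, but no infant number or accrual curve is given, older children randomized late are cut equally, and no Extension comparison by age is planned.

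Finally, Section 11.7 leaves definitions to the SAP, so some of this may be settled there.

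**Conclusion.** The point holds in limited form. Section 3.3 must be reconciled with itself and with Section 5.1.1.2; that rests on the text alone. The crude Extension incidence is not a risk over a defined period, because participants are at risk for about 1 to 10 months.

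The size is modest and depends on assumptions. With the earliest EOT date, 32 months of uniform accrual, full uptake and a constant hazard, about 28% lose some Extension time, and a risk of about 10% is reported roughly 0.5 SE low. Faster accrual enlarges this and a later EOT shrinks it to nothing. Late entrants bear most of it, and infants under 1 year are likely to be among them.

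The Extension is a single-arm, descriptive part of an unpowered study. The primary endpoint and the randomized Month 3 comparisons are not affected.

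**What to change.** 1. Reconcile the two statements in Section 3.3 with each other and with the offer in Section 5.1.1.2. Which stopping rule applies is for the sponsor to decide; the review takes no position.
2. In Sections 11.4.1.1 and 11.4.3.1, keep incidence and the annualized rate, and define the rate's person-time denominator. Add estimates at Months 6, 9 and 12 with numbers at risk: Kaplan-Meier for all-cause death, and cumulative incidence for bleeding, TE and TE death with other death as a competing event.
3. Report Extension exposure by age cohort.
4. Record the sponsor's EOT date as its own discontinuation reason. Section 5.6.3 lists none that fits; the nearest is termination of the study by the sponsor. This separates administrative from clinical stops.

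The cost is wording, one disposition code and one extra table, with no added subjects or visits. Confidence intervals at Month 12 will be wide. The new estimates assume independent censoring, which is reasonable for a calendar stop but less secure for discretionary stops; the separate code lets a reader judge how far that matters.
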